### Saving Instructions

**Each time you click 'Next' or 'Previous' your work is saved. You may click 'Save for Later' to save where you are and leave the form. Finally, if you jump to another page, using the dropdown at the top of the form, your work on each page will be saved. You will not be able to 'Check and Submit' form until all required fields are entered.**

### Project Title

The Impact of Text Messages on Anxiety and Health Promoting Behaviors Among Baccalaureate Nursing Students: A Mixed-Methods Approach

### Project Type

Dissertation Research

*\*ALL STUDENT PROJECTS MUST BE ACCOMPANIED BY A HUMAN SUBJECTS CITI TRAINING COMPLETION REPORT. PROTOCOLS FROM STUDENTS WILL NOT BE APPROVED UNTIL THIS ITEM IS RECEIVED*

### Department

Nursing and Allied Health Professions

**Will students be added at a later date.**

No

**Estimated project start date**

12/26/2017

*The project cannot start before IRB approval*

**Estimated project end date**

8/15/2018

*This date cannot be longer than a year from the start date. If you plan your project to go beyond one year you will need to submit a request for continuing review at the appropriate time.*

**Funding Information**

### Project Funding Source

**Entered:** 12/18/17 **By:** [REDACTED] **Internal:** No

I am planning to apply for the Graduate School Research Grant Spring of 2018 to help off set the cost of the one tool. However, the proposals are not due until March 2018.

**Entered:** 01/03/18 **By:** [name] **Internal:** No

If you are awarded a Graduate School Research Grant, you will need to amend your Informed Consent to explicitly state that "This research is partially funded by an IUP School of Graduate Students and Research Grant."

Non-funded research

*Please check all that apply*

### Combined Funding Source

Non-funded research

### Project Description

#### Purpose of the study

The purpose of this study is to examine if the inclusion of text messages related to self-care practices education in senior-level pre-licensure baccalaureate nursing curricula reduces state anxiety and improves the health-promoting behaviors of stress management and interpersonal relations.

*In a few sentences, describe the purpose of the study. This section need not be elaborate, but does need to clearly indicate the purpose of the study in a way that is clear to persons not familiar with the project.*

## Background of the study

Pre-licensure baccalaureate nursing students undergo a significant amount of stress throughout a nursing program. However, pre-licensure baccalaureate nursing students receive education on the theoretical content on self-care practices for patients but oftentimes do not utilize these practices to manage their own anxieties. Self-care practices are typically taught throughout the baccalaureate curricula. According to the Essentials of Baccalaureate Education for Professional Nursing Practice, the baccalaureate nursing graduate should be able to provide self-care instruction to others (American Association of Colleges of Nursing [AACN], 2008). Nursing students learn the application of self-care practice education for their patients and communities. However, many nursing students lack experience with personal self-care and health promotion (Nevins & Sherman, 2016), and may not be applying the practice of positive self-care strategies to help manage their own anxiety (Ashcraft & Gatto, 2015). In a recent study, nursing students who participated in a self-care course identified the need to provide self-care for themselves, learned about the application in their personal and professional lives, felt empowered to educate and advocate for their patients, and recognized the need to retain the knowledge for the future (Padykula, 2017). Additional studies have stated that nursing students who engage in self-care activities enjoy learning these practices (Blum, 2014), report both lower levels of stress (Drew et al., 2016), and lower levels of anxiety (Kang, Choi, & Ryu, 2009). Even with this knowledge, nursing students are at-risk for developing maladaptive coping strategies to stress. In fact, Drew et al. (2016) concluded that nursing students engage in less self-care practices as they progress through a nursing program and recommended that self-care practices be reinforced throughout the nursing curriculum.

Nursing students have reported that insufficient information, money, and rest have limited their ability to engage in positive health-promoting behaviors (Bryer, Cherkis, & Raman, 2013). Baccalaureate nursing students report that stress, anxiety, and time commitments are barriers to self-care behaviors in nursing school, even though they would like to improve their well-being with adequate sleep, exercise, diet, and hydration (Nevins & Sherman, 2016).

Unfortunately, nursing students who are unable to manage their anxiety may develop low levels of self-confidence which can negatively impact their ability to learn. Anxiety can impair learning which leads to poor performance in the clinical environment (Cheung & Au, 2011; Melincavage, 2011; Melo et al., 2010; Nielsen & Harder, 2013), decrease levels of self-confidence (DeBrew & Lewallen, 2014), and contribute to low levels of self-efficacy (Watt et al., 2016). Additionally, nursing students who are unable to manage their anxiety are at-risk for clinical failure, hinder faculty-student and patient-student interactions, and present themselves as unprofessional and unsafe (DeBrew & Lewallen, 2014; Killiam, Luhanga, & Bakker, 2011). These negative outcomes can impact nursing students' ability to flourish throughout a nursing program and as they transition into the workforce. Poor role transition by newly graduated nurses could contribute to burnout, poor job performance, dissatisfaction, and departure from the nursing profession (Cheng, Liou, Tsai, & Chang, 2015; Unruh & Nooney, 2011). Newly graduated nurses are vital for the nursing workforce because they fill the gaps in the nursing shortage. Furthermore, with the anticipated rise in the geriatric population over the next decade healthcare providers will be needed in even greater numbers making it critical that the healthcare workforce retains registered nurses. Therefore, nurse educators need to educate, reinforce, and support nursing students' practicing positive self-care throughout the program so that they are equipped with these skills after graduation. Sending SMS messages to pre-licensure baccalaureate nursing students would be a valid approach to support the students to

*This section should provide the reader with the administrative and/or scholarly context from which the project emerges. The section should contain enough information to provide Board members with no expertise in your discipline an understanding of how/why the use of human participants is warranted. This can often (but not always) be accomplished in one single spaced typed page or less. It is important to provide relevant citations and complete references so that the Board can conduct any necessary review of these foundations.*

reduce anxiety and improve the health-promoting behaviors of interpersonal support and stress management.

**What method(s) or design feature(s) do you plan to use in this study? Please choose all that apply**

Experimental Group  
Questionnaire  
Social Media  
Survey

*This information is used only for internal record keeping and quick identification. Simply mark those methods/design features you currently plan to use.*

**Subject Population**

**Age Range**

18 years or older

*State the anticipated age range. If it is your intention to exclude minors (those 17 and under), please say so explicitly.*

**Gender**

All

**Inclusion Criteria**

- (1) enrollment in a traditional pre-licensure baccalaureate nursing program in the Mid-Atlantic region
- (2) current enrollment in a senior-level nursing course with a clinical component with an anticipated graduation in May or August of 2018
- (3) Over the age of 18
- (4) English-speaking
- (5) Have a mobile device that is able to receive text messages

**Exclusion Criteria**

- (1) Enrollment in an RN to BSN program, Accelerated BSN program, or 3 year BSN program
- (2) Enrollment in a junior-level, sophomore-level nursing course with a clinical component or are enrolled in a senior-level nursing course without a clinical component or anticipate graduation after August 2018
- (3) Under the age of 18
- (4) Exclusively non-English speaking
- (5) Do not have access to a mobile device that is able to receive text messages

**Protected population and sensitive subjects: Indicate if any Human Subjects from the following list will be involved in the proposed activity:**

*No answer provided.*

### **Vulnerable Subjects**

No vulnerable subjects will be used in this study.

*If it is your intention to use vulnerable subjects, justify the importance of their use. Here and throughout the protocol discuss how their vulnerability will be matched with appropriate safeguards. The IRB web page discusses vulnerable subjects in more detail.]*

### **Methods and Procedures**

#### **Methods and Procedures**

*This is arguably the most important section of the protocol. You should complete this section in such a way that all of the research procedures are clear. Do not assume that any parts of the procedure can be inferred, and compose this section as though you were writing instructions that someone else could follow to conduct the project.*

## Method of Subject Selection

The setting for this study will be up to six public or private universities located in the Mid-Atlantic region. All potential schools of nursing have a traditional four-year baccalaureate degree in nursing program. The potential schools were identified through a review of the NCLEX-RN Performance of First Time Candidates Educated in Pennsylvania who Completed NCLEX in the U.S. published by the National Council of State Boards of Nursing. Nursing programs who had at least 50 graduates who were eligible to take the NCLEX in 2017 will be recruited. In Pennsylvania, 24 schools of nursing are eligible to be recruited based on these requirements. From the 24 schools of nursing in Pennsylvania, eight nursing schools were excluded because they have a PhD program. Pennsylvania State University has multiple campuses that offer traditional BSN programs. Two of the campuses will be excluded because they offer PhD programs (University Park & Hershey). However, this leaves five satellite campuses that may be recruited from. If none of these 16 schools of nursing are agreeable to participate, the researcher will look to other traditional baccalaureate nursing schools in the Mid-Atlantic region.

An email will be sent to the nursing chairs or faculty contact at each of the 16 eligible schools of nursing in Pennsylvania. The email will describe the research study purpose, timeline, and ask if the nursing chair or faculty contact would be interested in being a study site. If the nursing chair or faculty contact is agreeable, an in-person or telephone meeting will be offered to discuss the project. The first six schools of nursing who are agreeable to participate will be used for the study. Site approval or site IRB approval will be completed at each institution.

The researcher will go to each school in-person, provide a Zoom session, or offer to pre-record a video to introduce the study and provide the initial link to the pre-licensure senior-level baccalaureate nursing students. If the school would rather have the nursing secretary or site designee at the school distribute an initial email, the researcher will provide a pre-recorded video to explain the study. Student recruitment will start at the beginning of the Spring semester of 2018.

A power analysis was conducted to estimate the sample size required for the quantitative data analysis. According to Polit and Beck (2012), many nursing research studies utilize an effect size between .20 to .40 to determine the relationship between independent and

*Provide complete information about how research subjects will be identified, recruited, invited to participate, etc. Indicate approximately how many research subjects you will contact and how many you will actually use in your research. Your description of recruitment and selection must include any letters, announcements, advertisements, or other related materials. Any materials used in any selection/recruitment context should be included in the "Attachments" section below. Please see the IRB website for more information regarding how to protect the privacy, dignity, and welfare of potential subjects.*

dependent variables within the study population. Therefore, a medium effect size of .30 will be used. The standard significance level of 5% and .80 for power will be used (Polit & Beck, 2012). Based on an effect size of .30, significance level of 5%, and a power of .80, a sample size of 72 study participants was computed using G\*Power Version 3.1.9.2. Therefore, it is anticipated that nursing students from up to six public or private institutions in the Mid-Atlantic region will be recruited. The attrition of study subjects needs to be addressed due to the three data collection time points. The attrition of study subjects is common in a longitudinal study and is rarely 0% (Polit & Beck, 2012). Therefore, an attrition rate of 20% was computed for this study indicating that 14 additional study participants, for a total of 86 study participants, would need to be recruited to overcome anticipated attrition over the study timeframe. The sampling plan projection appears to be sufficient to obtain the needed sample. The researcher is attempting to recruit 100 pre-licensure senior-level baccalaureate nursing students from multiple sites. (I have attached a document to outline this process).

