## Methods and Procedures Applied to Human Subjects

**Entered:** 01/03/18 **By:** [name] **Internal:** No

In addition to listing each university's resources to provide participants after each data collection period, please include some national resources as well (hotlines, websites, etc.).

**Entered:** 01/03/18 **By:** [REDACTED] **Internal:** No

I have added a sentence : "In addition to the university resources, national resources such as hotlines and websites will also be included that focus on stress and anxiety."

After initial correspondence and site approval/IRB approval obtained then the researcher will arrange a time to introduce the study. The researcher will offer to come to each school to introduce the study or offer a Zoom or pre-recorded video to introduce the study to the pre-licensure baccalaureate nursing students. The researcher will provide the link to the nursing students or the nursing department designee may send the initial email invitation to the nursing students. The researcher will not be able to identify who received the initial email invitation to participate in the study. Student recruitment will start at the beginning of the Spring semester of 2018. The two group experimental design will collect data over the course of the spring academic semester. There will be three separate points of data collection. This is explained below.

Senior-level pre-licensure baccalaureate nursing students will access Qualtrics® via a link provided by the email invitation or offered by the researcher in person, Zoom, or on a pre-corded video. Implied consent will be established if a nursing student selects "yes" on the consent page in Qualtrics®. Contact information for the researcher and dissertation chair will be made available on the informed consent on Qualtrics®. After reviewing the consent and indicating intent to participate, potential study participants will then proceed directly survey tools. There are three data collection time periods within the study (1st two weeks of the semester, after the 5th text message, and within the last month of the semester). The two main tools used in the study have been found to be valid and reliable: The State-Trait Anxiety Inventory and the Health-Promoting Lifestyle Profile-II. I have attached the demographic questionnaire, HPLP-II, and the open-ended questions. Here is a breakdown of the tools used during each of the three data collection time periods:

The first two weeks of the semester:

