Nursing students will be reminded that their participation is voluntary throughout the study and they have the right to withdraw from the study at any time. The nursing department designee will send a reminder email within 72 hours of the initial study invitation. For the second and third data collection times, senior-

level pre-licensure baccalaureate nursing students will have 72 hours to complete the tools. After the 72 hours, an email reminder will be sent to the study participants to complete the tools within the next 72 hours for the second and third distribution. Since the email addresses will not be known for the first data collection time, an email reminder can not be sent. Study participants will have one week to complete the instruments from the initial email distribution. Qualtrics® is a password protected online survey program. The researcher will create the surveys, reminders, and text messages in Qualtrics® and will hand over the distribution to the ARL. The ARL will distribute and have access to the data and email addresses and will link the responses during the study period. During this time, the researcher will not have access to the data and will receive a de-identified file with the study data merged from the ARL. Throughout the study, the identifiable information will remain anonymous to the researcher. Additionally, the phone numbers and email addresses will also remain anonymous to the researcher.

The randomization of schools will be established prior to the first data collection. Each school will be considered a unit and will be randomized to either the intervention or control group. After the initial data collection, pre-licensure baccalaureate nursing students randomized to the intervention will receive text messages distributed from Qualtrics® throughout the semester.

The researcher anticipates 10 text messages will be sent to the senior-level pre-licensure baccalaureate nursing students. Nursing students will not receive any in-person or online form of education. The text messages will be no longer than 160 characters and will be created from the ANA's book *Self-Care and YOU: Caring for the Caregiver* (Richards, Sheen, & Mazzer, 2014). The messages were reviewed by a content expert. The text message will be sent from Qualtrics® by using a carrier text message. The email messages and distribution times will already be loaded into Qualtrics® prior to the ARL taking over the distribution.

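### Schools are randomised, but the 72-student calculation has no clustering term, so 72 (or about 80) students in six schools do not give the stated 80% power

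*Protocol*

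**What the plan says.** **Design** (Protocol, Methods and Procedures Applied to Human Subjects). "The two group experimental design will collect data over the course of the spring academic semester". "There will be three separate points of data collection". On assignment: "Each school will be considered a unit and will be randomized to either the intervention or control group".

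**Number of units** (Protocol, Method of Subject Selection). "The setting for this study will be up to six public or private universities". The split of schools between arms is not given.

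**Sample size** (same section). "Therefore, a medium effect size of .30 will be used". "The standard significance level of 5% and .80 for power will be used". The result, from G*Power: "Based on an effect size of .30, significance level of 5%, and a power of .80, a sample size of 72 study participants". A 20% attrition allowance adds 14 students, for a total of 86, and the recruitment aim is 100. The test, the effect-size metric, the sidedness and any repeated-measures correlation are not named. Schools appear in this paragraph only as the place where students will be found.

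**The concern.** When schools are randomised, the comparison of arms carries the variation between schools as well as between students, and that variation is estimated from the number of schools. Here there are at most six. A calculation that uses only effect size, alpha and power describes a trial that randomises individual students.

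Clustering is plausible. Students in one programme share faculty, placements and an exam calendar, and the outcomes include state anxiety over a single semester. Two things are at stake. The stated power would be too high, so a null result would be over-read. And if the analysis followed the same student-level logic, a difference between schools could be reported as an effect of the messages.

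**Working it through.** **1. Reproducing 72.** The figure does not follow from the stated inputs alone. A two-group ANOVA with f = .30 needs 90 students (power .709 at 72). Two routes give exactly 72, each with one added input:
- Repeated-measures between-groups test, f = .30, three time points, assumed correlation ρ = .70: λ = f²·N·k/(1+(k−1)ρ) = .09×72×3/2.40 = 8.10, power .801.
- One-sided t-test at d = .60 (f = .30), 36 per arm: noncentrality .60×√18 = 2.546, power .809.

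Both treat students as independent.

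**2. Anchor.** So as not to depend on the route, take the effect that 72 independent students detect with exactly 80% power, two-sided 5%, 70 df. Its noncentrality is δ = 2.841 (δ² = 8.07).

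**3. Clustering.** Assumptions: six schools, three per arm, equal sizes, no baseline adjustment. The protocol gives no ICC, so a range is shown. With N completers, m = N/6 and

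DE = 1 + (m−1)×ICC; δ_c = 2.841×√((N/72)/DE).

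The contrast of school means has 6 − 2 = 4 df, with critical value t = 2.776 (1.994 on 70 df).

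| ICC | DE, N = 72 | Effective N | δ_c | Power, 4 df, N = 72 | Power, 4 df, N = 80 |
|---|---|---|---|---|---|
| 0 | 1.00 | 72 | 2.841 | .575 | .618 |
| .01 | 1.11 | 65 | 2.696 | .534 | .571 |
| .05 | 1.55 | 46 | 2.282 | .414 | .435 |
| .10 | 2.10 | 34 | 1.960 | .325 | .337 |

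N = 80 is 100 recruits less 20%. The ICC 0 row shows that the loss does not rest on the choice of ICC: with 4 df it is already present. A simulation of 6 × 12 students with a t-test on school means gave .532, .413 and .327 at ICC .01, .05 and .10.

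**4. Detectable effect.** On 4 df, 80% power needs a noncentrality of 3.761. Relative to the planned effect, the detectable effect is (3.761/2.841)×√DE = 1.32×√DE, that is 1.4, 1.65 and 1.9 times at ICC .01, .05 and .10 with 72 completers.

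**5. If school were ignored.** Type I error ≈ 2×(1 − Φ(1.96/√DE)) = .063, .115 and .176 at ICC .01, .05 and .10. Simulated values were .063, .118 and .178.

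**6. Fewer schools.** The cap of six permits fewer. With four schools of 18 students (2 df), power is at most .359, at ICC 0.

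**The case against.** **Could no six-school trial reach 80%?** A reader might infer this, but it does not follow. On the same 4-df method, 27 completers per school (162 in all) give 81% at ICC .01, and 36 per school (216) give 80% at ICC .02. Programmes are recruited only if they have at least 50 graduates, so such class sizes are conceivable. The point holds for the numbers planned: 72, or about 80 from 100 recruits. At ICC .05 no number of students suffices with six schools (ceiling 78%).

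**Baseline adjustment could recover precision.** This stands. If the planned effect refers to an unadjusted follow-up score, and baseline correlates .5 to .7 with it (assumed), 4-df power with 72 completers rises to 65–80% at ICC .01 and 52–67% at ICC .05. Only the most favourable corner reaches 80%. The protocol states no adjustment, and the gain would differ if 72 came from a repeated-measures test. The figures above should therefore not be pasted into the protocol as its new power.

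**The test behind 72 is unknown.** Also true, and the size of the loss depends on it. On the one-sided route, 4-df power is 67% at ICC 0 and 52% at ICC .05. The power paragraph also mentions an attached document that is not shown. Independence is inferred from the listed inputs and from the routes that return 72.

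**Student-level degrees of freedom would look better.** With 80 completers and ICC .01 they give about 80%, but that disregards that six units were randomised. At ICC .05 they give only 64%.

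**Will false positives be inflated?** The protocol does not establish this. It names no outcome analysis, and the model may properly be left to an analysis plan. The type I figures are conditional on school being ignored.

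**Will the school identifier be lost?** Privacy/Confidentiality describes removal of email and phone only, so this cannot be inferred. It is merely unconfirmed.

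**Conclusion.** The mismatch between the randomised unit and the power calculation is explicit in the protocol. No choice of model in an analysis plan makes the 80% statement correct as derived. For 72 to 80 completers in six schools, unadjusted 4-df power is about 58–62% at best (ICC 0) and about 33–34% at ICC .10.

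These magnitudes are illustrative. They rest on a 3:3 split, equal school sizes, a two-sided test, no baseline adjustment, an assumed ICC, and an effect anchored to 80% power with 72 independent students. The direction is firmer than the size: without a baseline gain, six units reduce the power of the arm comparison even with no intraclass correlation.

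**What to change.** 1. Withdraw the 80% power statement. Restate power, or the detectable effect, for the actual number of schools over a stated ICC range. Compute it for the analysis that will be used, naming the test, effect metric and sidedness, and the assumed baseline correlation if baseline is a covariate.
2. Compare arms at the level of the randomised unit. Either use a mixed model with a school random intercept, the baseline score as covariate and small-sample degrees of freedom, or a t-test on school means. Details may sit in the analysis plan. Small-sample degrees of freedom such as Kenward-Roger are estimated and need not equal 4, so the restated power must match the method chosen.
3. Confirm that the Applied Research Lab keeps a coded school identifier in the de-identified file, before the file is released.
4. Report estimates with confidence intervals, and do not describe the comparison as 80%-powered.

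Cost: wording in the protocol and analysis plan, one recalculation, and at most one coded column. No extra students are required. The downside is a less favourable stated power.

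### The 20% attrition allowance is added to 72 instead of dividing 72 by 0.80, so the stated recruitment minimum of 86 leaves about 69 completers; 90 are needed

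*Protocol*

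**What the plan says.** The sample-size paragraph under Method of Subject Selection proceeds in four steps.

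- **Inputs to the power analysis.** "Therefore, a medium effect size of .30 will be used", and "The standard significance level of 5% and .80 for power will be used".
- **Required sample.** From these, "a sample size of 72 study participants was computed using" G*Power.
- **Attrition allowance.** The reason given is that "The attrition of study subjects needs to be addressed due to the three data collection time points". The allowance follows: "an attrition rate of 20% was computed for this study indicating that 14 additional study participants, for a total of 86 study participants". The paragraph presents this total as the recruitment that makes up for losses during the study.
- **Recruitment aim.** The paragraph judges the sampling projection sufficient and ends by saying that "The researcher is attempting to recruit 100 pre-licensure senior-level baccalaureate nursing students from multiple sites".

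The protocol thus gives three numbers: 72 required for analysis, 86 to be recruited so that attrition does not erode the 72, and 100 as the working aim.

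**The concern.** The 86 is put forward as the number that protects the 72 against a 20% loss. It looks like 72 increased by 20%. That is a different calculation from the number which, reduced by 20%, returns 72. Attrition is a proportion of those who enrol, and the paragraph itself ties it to enrolled students dropping out across the three surveys.

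At stake is whether the protocol's stated minimum meets its own requirement under its own attrition assumption. If it does not, recruitment could be judged complete at a number that the plan's own figures predict will fall short. Losses do reduce the data available: under Protection Against Risks, the data of a student who withdraws are destroyed and not used, so a formal withdrawal removes even the baseline responses.

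**Working it through.** **Inputs, all from Method of Subject Selection**

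- Required sample: n = 72, taken as given
- Attrition: d = 0.20
- Stated addition and total: 14 and 86
- Recruitment aim: 100

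**Step 1. Reproduce the plan's figure.** Adding 20% of the required sample:

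- n × d = 72 × 0.20 = 14.4, taken as 14
- 72 + 14 = 86 (unrounded, 72 × 1.20 = 86.4)

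This is exactly what the protocol states, so the method used was n × (1 + d).

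**Step 2. Apply the plan's attrition to the plan's total.**

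- 86 × (1 − 0.20) = 68.8, about 69 completers
- Shortfall: 72 − 68.8 = 3.2, about 3 students
- Largest attrition that 86 can absorb: 14/86 = 16.3%, not 20%

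**Step 3. Calculate the number that does leave 72.** Solve N × (1 − d) = n for N:

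- N = n/(1 − d) = 72/0.80 = 90
- Additional students: 90 − 72 = 18, not 14
- Check: 90 × 0.80 = 72
- Understatement of the minimum: 90 − 86 = 4

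**Step 4. Check the aim of 100.** 100 × 0.80 = 80 completers, which exceeds 72.

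**Step 5. Effect on power.** The protocol names no test, effect-size metric, sidedness or correlation. I therefore assume only that the test is two-sided at 5%, that it has 80% power at 72 completers, and that a normal approximation holds. The noncentrality at 72 is then 1.960 + 0.842 = 2.802, and it scales with the square root of the number of completers:

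| Completers | Noncentrality | Power |
|---|---|---|
| 72 | 2.802 | 80% |
| 68.8 | 2.802 × √(68.8/72) = 2.739 | Φ(2.739 − 1.960) = 78% |
| 80 | 2.802 × √(80/72) = 2.953 | Φ(2.953 − 1.960) = 84% |

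A t-based version (noncentrality 2.841 at 72, n − 2 degrees of freedom) gives the same rounded values.

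**Step 6. Chance of reaching 72.** As a further illustration, assume each recruited student independently stays with probability 0.80. The number of completers is then binomial:

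| Recruited | Expected completers | P(at least 72) |
|---|---|---|
| 86 | 68.8 | 0.24 |
| 90 | 72 | 0.56 |
| 100 | 80 | 0.98 |

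Ninety is the number that meets 72 on average. It does not guarantee 72.

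**The case against.** The strongest reply accepts the arithmetic and disputes its weight. The same paragraph sets a recruitment aim of 100, which leaves about 80 completers and makes reaching 72 very likely (0.98 in Step 6). Nothing in the protocol makes 86 a cap or a stopping point. Even in the worst case the loss is about 3 students and 2 points of power. On this view the 86 is an intermediate figure with no effect on conduct or budget.

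Most of that stands, and it is why the point is small. It does not make the figure right. The 100 is only something the researcher is trying for, whereas the 86 is presented as what is needed. Enrolment depends on up to six schools agreeing and on volunteers within them. A final total of 86 to 89 would satisfy the stated requirement while the plan's own attrition rate predicts fewer than 72 completers.

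A second reply is that correcting 86 to 90 refines a number whose base is unsettled. The 72 cannot be checked uniquely because the test behind it is not named. Schools, not students, are randomised (Methods and Procedures Applied to Human Subjects), and the sample-size paragraph mentions no allowance for clustering. That is fair as a limit on what 90 means: it leaves 72 completers, and whether 72 completers give 80% power is a separate question. The attrition step takes the 72 as given, so it is wrong whatever the answer to that question.

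**Conclusion.** The error is certain on the document's own numbers. The stated minimum of 86 does not survive 20% attrition with 72 students left: it leaves 68.8 and should be 90. The minimum is understated by 4 and the expected shortfall is about 3 completers. The cost is about 2 points of power, from 80% to 78%, for any two-sided 5% test that has 80% power at 72.

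If the aim of 100 is met, there is no shortfall. The exposure is confined to a recruitment total of 86 to 89. The sentence should be corrected, but the point does not threaten the study.

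The correction from 86 to 90 rests only on the 72 and the 20% that the protocol states. The power figures and the probabilities of reaching 72 rest on the further assumptions named in Steps 5 and 6.

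**What to change.** In Method of Subject Selection, replace the 14 additional participants and the total of 86 with 18 additional participants and a total of 90, and show the calculation (72/0.80 = 90). Keep the aim of 100 and add that it leaves 80 completers at 20% attrition. State that the 90 is conditional on the 72, so that it is recalculated as n/(1 − 0.20) if the required sample is revised.

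The cost is one sentence. The existing aim already exceeds 90, so the recruitment aim, design and budget do not change.
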